4.1 Description of study design

This is an open-label, phase II, randomized, multi-center, pilot study to assess the efficacy in terms of erythroid improvement of DFX combined with EPO compared to EPO alone in patients with low- and int-1-risk MDS.

Patients will be randomly assigned to DFX plus EPO 40,000 units/week or to EPO 40,000 units/week alone in a 1:1 ratio. The dose of DFX DT will be 10 mg/kg/day and the dose of DFX FCT will be 7 mg/kg/day. At the time when DFX FCT study drug becomes available at a study site, all new patients who are randomized to combination therapy will receive the DFX FCT. Patients who are ongoing and receive DFX DT will continue with the DT. It is not permitted to change formulation during treatment. EPO dose changes after 4 and 12 weeks of study treatment will also be performed in both arms according to the EPO guidelines.

If after 4 weeks, increase in Hb is < 1 g/dL and total Hb is < 12 g/dL, the EPO dose will be increased to 60,000 units/week. If increase in Hb is ≥ 1 g/dL and total Hb is < 12 g/dL, patients will continue the current EPO dose. If Hb increase is ≥ 1 g/dL and total Hb is ≥ 12 g/dL, the patients will hold EPO treatment until end of study (Table 4-1).

If after 12 weeks of treatment with EPO alone, Hb increase is < 1 g/dL and total Hb is < 12 g/dL, the patient will switch to the combination therapy with EPO and DFX. If increase in Hb is ≥ 1 g/dL and total Hb is < 12 g/dL, patients will continue the current EPO dose. If Hb increase is ≥ 1 g/dL and total Hb is ≥ 12 g/dL, the patients will hold EPO treatment until end of study (Table 4-1).

[figure not shown]
If after 12 weeks of treatment with EPO in combination with DFX, Hb increase is < 1 g/dL and total Hb is < 12 g/dL, the patient will be discontinued from the study. If increase in Hb is ≥ 1 g/dL and total Hb is < 12 g/dL, patients will continue the current EPO dose plus DFX. If Hb increase is ≥ 1 g/dL and total Hb is ≥ 12 g/dL, the patients will hold EPO dose and receive treatment with DFX alone.

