	Hb increased < 1 g/dL from baseline and Hb < 12 g/dL	Increase EPO to 60,000 units/week *
	Hb increase is ≥ 1 g/dL and Hb < 12 g/dL	Continue EPO 40,000 units/week *
	Hb increase is ≥ 1 g/dL and Hb ≥ 12 g/dL	Hold EPO treatment *
Week 12	Hemoglobin status	Action
	Hb increased < 1 g/dL from baseline and Hb < 12 g/dL	If patient is in the combination arm: Discontinue from the study or If patient is in the EPO monotherapy arm: Switch to the combination EPO + DFX
	Hb increase is ≥ 1 g/dL and Hb < 12 g/dL	Continue current EPO dose *
	Hb increase is ≥ 1 g/dL and Hb ≥ 12 g/dL	Hold EPO treatment *

* Patients in combination arm will continue DFX DT 10 mg/kg/day or DFX FCT 7 mg/kg/day treatment

[figure not shown]
The primary objective (erythroid response according to IWG criteria: Hb increase ≥ 1.5 g/dL) will be assessed at 12 weeks of treatment. At any time, if Hb ≥ 12 g/dL, EPO will be stopped until the end of study.

At 24 weeks, patients initially assigned to the combination therapy who showed Hb increase ≥ 1 g/dL at week 12 will be assessed for full hematological response according IWG criteria (Erythroid response: Hb increase from baseline ≥ 1.5 g/dL; Neutrophil response: increase from baseline of ≥ 100% and > 0.5 x 10⁹/L; Platelet response: increase from baseline of ≥ 30 x 10⁹/L). Patients initially treated with EPO alone and switched to the combination therapy with EPO and DFX after 12 weeks will be assessed for erythroid response according to IWG criteria after 24 weeks.

No RBC transfusions are allowed after randomization, as transfusions would affect the endpoints of the trial. Patients who are RBC transfusion dependent must not be enrolled in the study. RBC transfusion dependence is defined as more than 2 units RBC /4 weeks at any time during the last 12 week period prior to study entry (Gale 2011). Patients must be withdrawn from the study anytime when transfusion as rescue therapy is needed.

Safety assessments are routinely performed including collection of AEs, SAEs, vital signs, physical examination, ECG, hematological and biochemistry assessments.

Patients will continue therapy until disease progression or intolerable toxicity, patient decision or death, after 12 weeks of combination treatment without response or after 24 weeks treatment duration at which point an End of Treatment (EOT) Visit will be performed and the End of Treatment CRF page will be completed.

30 day follow-up

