6.1.4 Treatment duration

The whole treatment period will last 24 week. The primary objective (erythroid response according to IWG criteria: Hb increase ≥ 1.5 g/dL) will be assessed by 12 weeks of treatment. At any time, if Hb ≥ 12 , EPO will be stopped until the end of study. These patients will be considered as responders.

By 24 weeks, patients initially assigned to the combination therapy who showed Hb increase ≥ 1 g/dL by week 12 will be assessed for full hematological response according IWG criteria (Erythroid response: Hb increase from baseline ≥ 1.5 g/dL; Neutrophil response: increase from baseline of $\geq 100\%$ and $> 0.5 \times 10^9/L$; Platelet response: increase from baseline of $\geq 30 \times 10^9/L$).

If after 12 weeks of treatment with EPO alone, Hb increase is < 1 g/dL and total Hb is < 12 g/dL, the patient will switch to the combination therapy with EPO and DFX for the remaining 12 weeks and will be assessed for erythroid response by 24 weeks. If after 12 weeks of treatment with EPO in combination with DFX, Hb increase is < 1 g/dL and total Hb is < 12 g/dL, the patient will be discontinued from the study.

Subjects need to be discontinued from the study if at least one of the following occurs:

- $\geq 50\%$ decrement from maximum response levels in granulocytes or platelets
- Reduction of Hb level ≥ 1.5 g/dL compared to best response
- Patient requiring blood transfusion at any time

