2.9.2.4 To assess iron parameters in patients randomized to EPO alone, DFX+EPO and in patients randomized to EPO alone and switched to DFX+EPO after 12 weeks

This analysis will include patients randomized either to EPO or DFX+EPO at baseline as well as patients who are non-responders to erythroid at week 12 in the EPO group switched to combination therapy. The time-course of serum ferritin and its absolute/relative changes from baseline will be summarized by descriptive statistics by visit and erythroid response. Data will be summarized on FAS.

Note: Patients randomized to EPO and not switching after 12 weeks to EPO+DFX, will consist of only responders.

2.9.2.5 To assess Hb parameters in patients randomized to EPO alone, DFX+EPO and in patients randomized to EPO alone and switched to DFX+EPO after 12 weeks

This analysis will include patients randomized either to EPO or DFX+EPO at baseline as well as patients who are non-responders to erythroid at week 12 in the EPO group switched to combination therapy. The time-course of Hb and its absolute/relative changes from baseline will be summarized by descriptive statistics by visit and erythroid response. Data will be summarized on FAS.

Note: Patients randomized to EPO and not switching after 12 weeks to EPO+DFX, will consist of only responders.

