S21	Epo dose reduced below assigned dose as per protocol for more than 1 week in period week 1-12	Report as PD, include in FAS and Safety Set.
S22	Epo dose reduced below assigned dose as per protocol for more than 1 week in period week 13-24	Report as PD, include in FAS and Safety Set.
S23	Epo dose increased above assigned dose as per protocol for more than 1 week in period week 1-12	Report as PD, include in FAS and Safety Set.
S24	Epo dose increased above assigned dose as per protocol for more than 1 week in period week 13-24	Report as PD, include in FAS and Safety Set
S03	Epo dose maintained at 40.000 units/week and not increased to 60.000 units/week after 4 weeks as per protocol for more than 1 week but Hb increase < 1 g/dL and total Hb < 12 g/dL	Report as PD, include in FAS and Safety Set.
S05	Epo dose increased to 60.000 units/week and not maintained at 40.000 units/week after 4 weeks as per protocol for more than 1 week but Hb increase ≥ 1 g/dL and total Hb < 12 g/dL	Report as PD, include in FAS and Safety Set.
S06	Patient randomized to monotherapy not switched to combination therapy as per protocol or switch delayed for more than 1 week after 12 weeks of treatment but Hb increase < 1 g/dL and total Hb < 12 g/dL	Report as PD, include in FAS and Safety Set.
D12	Patient randomized to combination therapy not discontinued after 12 weeks of treatment as per protocol or discontinuation delayed for more than 1 week but Hb increase < 1 g/dL and total Hb < 12 g/dL	Report as PD, include in FAS and Safety Set.
S10	Patient randomized to combination therapy stopped DFX treatment for more than 1 week in period week 1-12 not as per protocol	Report as PD, include in FAS and Safety Set.
S25	Patient assigned to combination therapy stopped DFX treatment for more than 1 week in period week 13-24 not as per protocol	Reported as PD, include in FAS and Safety Set.
M01	Forbidden concomitant medication as per	Report as PD,

	protocol	include in FAS and Safety Set.
M02	Patient received iron chelation therapy other than the study treatment	Report as PD, include in FAS and Safety Set.
D01	Transfusion during the study but not withdrawn	Report as PD, include in FAS and Safety Set.
D02	Pregnancy during the study, but not withdrawn	Report as PD, include in FAS and Safety Set.
S11	Patient randomized but received wrong study drug	Report as PD, include in FAS and Safety Set.

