4.6 Number of decimals

Whenever possible, minimum and maximum will be presented to the same precision as the raw data. Mean and median will be presented to one more decimal place and standard deviation to two more decimal places.

Unless stated otherwise, no imputation for missing data will be performed.

5 References

Agresti and Caffo (2000). Simple and Effective Confidence Intervals for Proportions and Differences of Proportions Result from Adding Two Successes and Two Failures. *The American Statistician*, Vol 54, No. 5.

Clopper, C. J., and Pearson, E. S. (1934), 'The Use of Confidence or Fiducial Limits Illustrated in the Case of the Binomial', *Biometrika* 26, 404–413.

6 SAS procedure used for inferential analysis

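### The by-visit Hb and ferritin summaries pool all combination patients up to week 12 with only those kept by the week-12 Hb rule after it, so the arm's mean Hb steps up once between weeks 12 and 16 without any patient improving

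*SAP*

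**What the plan says.** **The summaries.** SAP 2.9.2.5 covers patients randomized to either arm at baseline, plus the EPO patients who switch: "The time-course of Hb and its absolute/relative changes from baseline will be summarized by descriptive statistics by visit and erythroid response". SAP 2.9.2.4 matches it for ferritin: "The time-course of serum ferritin and its absolute/relative changes from baseline will be summarized by descriptive statistics by visit and erythroid response". In both, "Data will be summarized on FAS". Protocol 10.5.9 and 10.5.10 are parallel. On missing values, SAP 4.6 says "Unless stated otherwise, no imputation for missing data will be performed".

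**The week-12 rule.** For 12 weeks of combination treatment, protocol 4.1 says that if "Hb increase is < 1 g/dL and total Hb is < 12 g/dL, the patient will be discontinued from the study". Protocol Table 4-1 and SAP Table 2-1 repeat it: "If patient is in the combination arm: Discontinue from the study". SAP 4.4 makes non-adherence a reportable deviation (D12): "Patient randomized to combination therapy not discontinued after 12 weeks of treatment as per protocol". EPO patients meeting the same trigger switch treatment and stay in the study.

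**Other exits.** Protocol 6.1.4 also requires discontinuation at any time for "Reduction of Hb level ≥ 1.5 g/dL compared to best response", for a large fall in granulocytes or platelets, or for a transfusion need. Under protocol 7.1.3.1, nothing further is assessed after withdrawal.

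**A second description of the group.** The endpoint column of protocol Table 3-1 refers to patients who were in the combination arm throughout, whereas the objective column and SAP 2.9.2.5 refer to patients randomized.

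**The concern.** A mean-by-visit curve is read as the path of one group of patients. Here the group changes between weeks 12 and 16, and the change is decided by the variable being averaged. Patients with a small Hb rise contribute up to week 12 and then disappear from the combination arm, so the mean of those left is higher even if nobody's Hb moves.

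The curve could then be taken as evidence of further benefit from DFX+EPO beyond week 12, in a pilot whose later weeks are of obvious interest. Both SAP sections carry a note about who remains among the EPO non-switchers. Neither has a note on the loss from the combination arm.

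**Working it through.** The plan gives no figure for the Hb time course, so there is none to reproduce. Its only planning figures are illustrative confidence intervals for the response difference (protocol 10.8, SAP 2.11), which do not bear on this point. I take two response rates from them: the 40% reference, and 60% (reference plus 20 points).

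**Step 1: who meets the rule.** Entry Hb is below 10 g/dL, or up to 10.5 with the 5% tolerance (protocol 5.2). A rise below 1 from a baseline below 10.5 ends below 11.5. The Hb < 12 condition is then always met, and the rule reduces to a rise below 1 g/dL.

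**Step 2: whether leavers appear later.** The week-12 visit is Visit 10 (Days 77 to 91, nominal Day 84; SAP 4.2.11). A final visit is due as soon as possible, or within 2 weeks (protocol 7.1.3, 4.3): 84 + 14 = Day 98. Visit 11 opens on Day 105. Leavers therefore normally contribute nothing from Visit 11 on.

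**Step 3: size of the step.** Let X be the week-12 Hb change, normal with SD σ and mean μ set so that P(X ≥ 1.5) = p. Hb is held fixed after week 12.

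- μ = 1.5 − σ·z(1−p)
- a = (1 − μ)/σ; fraction leaving = Φ(a)
- step = E[X | X ≥ 1] − μ = σ·φ(a)/(1 − Φ(a))

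The documents do not give σ; I assume 1.0 to 1.5 g/dL.

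Example, p = 0.6, σ = 1.0: μ = 1.753, a = −0.753, Φ(a) = 0.226, φ(a) = 0.300, step = 0.300/0.774 = 0.39.

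Example, p = 0.4, σ = 1.5: μ = 1.120, a = −0.080, Φ(a) = 0.468, φ(a) = 0.398, step = 1.5 × 0.398/0.532 = 1.12.

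| Response | σ | Leave, of 30 | Mean, all | Mean, stayers | Step |
|---|---|---|---|---|---|
| 60% | 1.0 | 7 | 1.75 | 2.14 | 0.39 |
| 60% | 1.5 | 8 | 1.88 | 2.58 | 0.70 |
| 40% | 1.0 | 12 | 1.25 | 1.89 | 0.65 |
| 40% | 1.5 | 14 | 1.12 | 2.24 | 1.12 |

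**Step 4: the split by response.** Response needs 1.5 g/dL and staying needs 1.0. After week 12 the non-responder stratum keeps only rises of 1.0 to below 1.5, that is 30 × (1 − p − Φ(a)) patients.

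| Response | σ | Non-responders, all | Those staying | Step | Left, of 30 |
|---|---|---|---|---|---|
| 60% | 1.0 | 0.79 | 1.26 | 0.47 | 5.2 |
| 60% | 1.5 | 0.43 | 1.26 | 0.82 | 3.6 |
| 40% | 1.0 | 0.60 | 1.25 | 0.65 | 5.9 |
| 40% | 1.5 | 0.15 | 1.25 | 1.09 | 4.0 |

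In this model every responder stays, so that stratum has no step.

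**Step 5: sensitivity.**

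- *Response at any visit, with reading error.* I simulated a true change rising linearly to week 12 and then flat, with SD 1.0 to 1.5, error SD 0.4 to 0.5 per reading, and response counted at any visit to week 12. The pooled step is 0.46 to 0.81 g/dL at 60% and 0.74 to 1.28 at 40%. Responders move by −0.02 to −0.08. Non-responders jump by 0.64 to 1.27, with about 3 to 5 of 30 left. An earlier plateau makes the pooled step somewhat larger.
- *Imperfect correlation.* With a correlation of 0.8 between weeks 12 and 16 and no true change, the pooled step falls to 0.31 to 0.56 at 60% and 0.51 to 0.89 at 40%. The same stayers change by −0.08 to −0.23.
- *Against EPO (same model, identical true effects).* Combination stayers exceed all EPO-randomized patients by 0.31 to 0.89 g/dL, but differ from EPO non-switchers by about 0.

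**The case against.** The best counter-argument is that this is a secondary, descriptive summary in a pilot of about 60 patients, with no test attached. The number of patients is reported at each visit, so the loss is visible. The plan asks for a split by response, and the table shells are in a module not available here, so a pooled curve is not certain. All of that stands and limits the weight of the point. It does not remove it: a falling n shows that patients left, not that they left because of low Hb, and the split still leaves a jump in non-responders.

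If Table 3-1 means only patients who stayed, there is no step, because leavers are absent from every visit. That is a fair reading of the endpoint column. The curve would then be selected on outcome at all visits. SAP 2.9.2.1 says explicitly when it restricts to patients who remained in their arm; 2.9.2.5 does not.

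SAP 2.10.3 already gives change to the last available value at end of treatment for Hb and ferritin, which keeps leavers. It is on the Safety Set, and it mixes week-12 and week-24 values, so it is not a week-24 result for the randomized arm.

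A reader might also infer more than the documents support:

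- **A growing gain after week 12.** The week-12 rule produces one step; the same stayers then drift slightly down when the correlation is imperfect.
- **A general between-arm bias.** EPO non-switchers are selected by the same 1 g/dL cut, so the distortion arises only against all EPO-randomized patients.
- **A known ferritin bias.** The negative relationship in protocol 1.1 and 2.1 is between levels of Hb and ferritin, not changes from baseline.
- **Complete data up to week 12.** Relapse and transfusion exits can occur before then.

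**Conclusion.** The point holds. Followed as written, for patients randomized and on observed values, the plan gives a combination-arm mean Hb change that steps up between weeks 12 and 16 whenever at least one patient meets the week-12 rule and Hb is otherwise stable. The existence of the step follows from the documents; its size rests on assumption. With an SD of Hb change of 1.0 to 1.5 g/dL and stable true Hb after week 12, it is about 0.4 to 0.8 g/dL at 60% response and 0.65 to 1.3 at 40%, and smaller (0.31 to 0.89 across both rates) if readings correlate only 0.8. Responders show no material upward step. The non-responder stratum, reduced to about 3 to 6 of 30 patients, jumps by about 0.5 to 1.3.

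For ferritin the change of population is the same, but its effect on the mean cannot be signed. The primary analysis, which ends at week 12, is unaffected. This is a worthwhile, inexpensive correction to a secondary summary.

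**What to change.** In SAP 2.9.2.4 and 2.9.2.5:

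1. End the by-visit summary of all randomized patients at week 12.
2. Present weeks 16 to 24 in a separate table of patients continuing past week 12, with that cohort's own baseline and week-12 values and the number present at each visit. Footnote it as conditional on the week-12 Hb result.
3. State whether the combination group is everyone randomized or only those who stayed, and reconcile this with the endpoint column of protocol Table 3-1.
4. Optionally, add a FAS version of the change to last available value from SAP 2.10.3, labelled as last available value and not as week 24.

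The cost is SAP wording and one extra table from data already collected. The later part of the curve will look less favourable and will carry a caveat. No treatment or discontinuation rule needs to change.

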2.10 Safety evaluation

For all safety analyses, the Safety Set will be used. All listings and tables will be presented by treatment group.

2.10.1 Analysis set and grouping for the analyses

The overall study period will be divided into three mutually exclusive segments:

1. pre-treatment period: from day of patient's informed consent to the day before first dose of study medication

2. on-treatment period: from the day of first dose of study medication to 30 days after last dose of study medication
3. Post-treatment period: starting at day 31 after last dose of study medication.

If dates are incomplete in a way that clear assignment to pre-, on-, post-treatment period cannot be made, then the respective data will be assigned to the on-treatment period.

The assessment of safety will be based mainly on frequency of AEs and on the number of laboratory values that fall outside of pre-determined ranges.

The safety summary tables will include on-study assessments (with the exception being the prior concomitant medications, laboratory parameters with baseline value taken prior to start of study drug). All safety assessments will be listed and those collected outside of the on-study period will be flagged appropriately.

In all safety listings, a column will be added to provide the true treatment (EPO alone, EPO+DFX DT or EPO+DFX FCT, DFX DT or DFX FCT alone, no treatment) at onset of AE or at time of any other safety assessment and the original treatment assigned.

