As the EPO guidelines only provide guidance for EPO use (EPO dosing, dose adjustments and dose discontinuation) and do not specify any criteria for the evaluation of erythroid response in MDS patients, in this study, the primary objective erythroid response will be assessed according to IWG criteria (Hb increase ≥ 1.5 g/dL) at 12 weeks of treatment. At any time, if Hb ≥ 12 g/dL, EPO will be stopped until the end of study. Patients treated with the combination therapy will stop EPO if Hb ≥ 12 g/dL and continue on DFX.

At 24 weeks, patients initially assigned to the combination therapy who showed Hb increase ≥ 1 g/dL at week 12 will be assessed for full hematological response according to IWG criteria (Erythroid response: Hb increase from baseline ≥ 1.5 g/dL; Neutrophil response: increase from baseline of $\geq 100\%$ and $> 0.5 \times 10^9/L$; Platelet response: increase from baseline of $\geq 30 \times 10^9/L$).

Patients initially treated with EPO alone and switched to the combination therapy with EPO and DFX after 12 weeks will be assessed for erythroid response at study end after 24 weeks of study treatment.

Figure 4-1 Study Design

Pre-treatment phase (Screening)

At Screening Visit (Visit 1) the investigator or his/her designee will assign a unique number to patients being considered for the study.

Prior to performing any study-related procedures or assessments, the patient must provide written consent to participation in this study. A screening period (up to 28 days) will be used to assess patient eligibility. Two Screening Visits will be required because key safety parameters need to be performed twice before the first dose administration ([Table 7-1](#)).

This study will use an Interactive Web Response (IWR) technology for randomization. Once the patient provides a signed informed consent form and eligibility is confirmed (all inclusion/exclusion criteria have been verified) the investigator and/or his designee can register the patient using the IWR.

Treatment phase

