10.5.11.2 Adverse events (AEs)

Summary tables for adverse events (AEs) will include only AEs that started or worsened during the on-treatment period, the **treatment-emergent** AEs. However, all safety data (including those from the pre and post-treatment periods) will be listed and those collected during the pre-treatment and post-treatment period are to be flagged.

[figure not shown]
The incidence of treatment-emergent adverse events (new or worsening from baseline) will be summarized by system organ class and or preferred term, severity (mild/moderate/severe), type of adverse event, relation to study treatment by treatment group.

Deaths reportable as SAEs and non-fatal serious adverse events will be listed by patients and tabulated by type of adverse event and treatment group.

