2.7.1 Exposure to study treatment

For all analysis described in this section, the Safety Set will be used.

Duration of exposure

The *duration of exposure to study drug* is defined as the time interval from first (non-zero) dose of study drug administration to last study drug administration date (i.e. last known study drug administration date), and it will be calculated using the following formula:

Duration of exposure (days) = [(last date of exposure to the study drug) – (date of first administration of the study drug) + 1 day], where:

- ‘Date of first administration of the study drug’ is defined as the first date when a non-zero dose of study treatment is administered. For the sake of simplicity, the date of first administration of study treatment is referred to **start date of study treatment**.
- ‘Last date of exposure to the study drug’ is the date of last administration of this study treatment which is defined as the last date when a non-zero dose of study treatment is administered. This date will also be referred as **last date of study treatment**.

The duration of exposure includes the periods of temporary study drug interruption.

For patients who did not take any study drug, the duration of exposure is defined as zero.

The duration of exposure excluding the temporary study drug interruption will also be computed, only time interval where the drug was known to be taken will be considered. It will be computed using the following formula:

Duration of exposure excluding temporary study drug interruption (days) = Duration of exposure (days) – number of days during this time interval where the actual dose was zero.

Both the duration of exposure and duration of exposure excluding interruptions will be summarized as continuous variables and by days as <28, 28 to <56, 56 to <84, 84 to <140, 140 to <164 and ≥ 164 .

Percentage of exposure

The percentage of exposure is defined as $100 \times (\text{duration of exposure excluding interruptions}) / (\text{duration of exposure})$.

It will be summarized as a continuous variable and by the following categories as <20%, 20% to <40%, 40% to <60%, 60% to <80% and 80% to $\leq 100\%$.

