2.7.3 Dose reductions and interruptions

The number of patients with dose reductions or interruptions, as well as the reasons leading to study drug dose reduction or to study drug interruption will be tabulated.

The number of dose interruptions and dose reductions will be tabulated by treatment group. Both of dose reduction and dose interruption will be calculated with regards to DFX DT or DFX FCT and EPO. Patients randomized to EPO arm or EPO+DFX arm may have an AE related to either EPO and/or DFX and thus the drug may be stopped or the dose may be reduced till the AE severity reduces.

An **interruption** is defined as a dose equal to zero on one or more days as reported in the CRF. A missing dose will not be considered as zero. A zero dose will not be considered as an interruption if it is the last dose administration record for a patient.

An interruption during consecutive days for the same reason is counted once.

If an interruption occurs for more than one consecutive day due to different reasons, then it will be counted for each reason.

A **dose reduction** is defined as a decrease in dose from the protocol planned starting dose or a decrease from the previous non-zero dose, even if this decrease has been directly preceded by an interruption. If, due to a dosing error, a patient receives higher dose than protocol planned starting dose and moves down to the planned starting dose then this is not be counted as a reduction. However if they move directly from a higher than planned starting dose down to a lower than protocol planned starting dose, then this is counted as a reduction.

A **dose increase** is defined as an increase in dose from the protocol planned starting dose or an increase from the previous non-zero dose, even if this increase has been directly preceded by an interruption.

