4.2.3 Date of last administration of study drug

The date of last administration of study drug is defined as the last date when a non-zero dose of study treatment EPO or EPO+DFX DT or EPO+DFX FCT is administered and recorded on the DAR of the CRF. The date of last administration of study treatment is referred to **end date of study treatment or last date of study treatment**.

Note: For patients either randomized to EPO+DFX DT or EPO+DFX FCT or for patients who switch to EPO+DFX DT or EPO+DFX FCT after 12 weeks, the end date of study treatment could be the last date when a non-zero dose of DFX DT or DFX FCT is administered since EPO is administered weekly and the patient may have received the EPO 6 days before the last non-zero dose of DFX DT or DFX FCT is given.

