4.2.11 Visit Windows

A year = 365.25 days.

A month = 365.25/12=30.4375 days.

Month 1 = Day (1;45] and then floor(n×30.4375) days±15 days, n=2, 3, 4,... that is Month 2 = Day (45;75]; Month 3 = Day (75;106]; etc.

For each parameter (i.e., hematologic and erythroid response), time windows will be used to identify data to be considered for the specific analysis at a specific time point. If there is more than one assessment within the time window, the last available assessment in that time window will be used. For all windows after baseline, only values after first dose of study drug will be used. Time windows are defined based on date of randomization (=study day 1; Visit 3 according to VES of protocol).

The following table shows the time windows for the analyses of responses based on planned assessment schedule.

Table 4-1 Visit windows

Planned assessment	Time window	Nominal day for visit
Baseline	Baseline; see definition 4.2.6	Baseline
Visit 3: Date of Randomization	Day 1	Day 1
Visit 4	Day 4 to Day 10*	Day 7
Visit 5	Day 11 to day 17*	Day 14
Visit 6	Day 18 to Day 24*	Day 21
Visit 7	Day 25 to Day 31*	Day 28
Visit 8	Day 35 to Day 49*	Day 42
Visit 9	Day 50 to Day 63*	Day 56
Visit 10	Day 77 to Day 91*	Day 84
Visit 11	Day 105 to Day 119*	Day 112
Visit 12	Day 133 to Day 147*	Day 140

The End of Treatment visit time window is Day 161 to Day 175 with nominal day of visit is Day 168 considering Visit 3 as Day 1.

In case of early treatment discontinuation or end of visit 12, the follow up will be 27-33 days from the last date when a non-zero dose of study treatment is administered (Last date of study treatment).

Considering, a patient has received EPO only and received a response. This patient will hold EPO until study end. However, Follow-up visit for them will be 30 days (+/- 3 days after EOT) and not 27-33 days from the last date when a non-zero dose of study treatment is administered.

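### The AE summary window closes 30 days after the last non-zero dose, so the same EPO hold at Hb ≥ 12 g/dL gives EPO-alone patients a shorter counted period than combination patients

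*SAP*

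**What the plan says.** - **Window.** SAP 2.10.1 defines the "on-treatment period: from the day of first dose of study medication to 30 days after last dose of study medication"; protocol 10.5.11.1 has the same rule. SAP 4.2.3 says that the last administration "is defined as the last date when a non-zero dose of study treatment EPO or EPO+DFX DT or EPO+DFX FCT is administered". Under SAP 2.7.3, "A zero dose will not be considered as an interruption if it is the last dose administration record for a patient", so a hold that runs to the end of the record does not move that date.
- **What is tabulated.** Protocol 10.5.11.2: "Summary tables for adverse events (AEs) will include only AEs that started or worsened during the on-treatment period". Later AEs are listed and flagged. SAP 2.10.2 restricts its tables to an *on-study* period, which it equates with treatment-emergent AEs and never defines.
- **The hold.** Protocol 4.1 and 6.1.4 stop EPO at any time that Hb reaches 12 g/dL, until the end of study. For the other arm, protocol 4.1 adds: "Patients treated with the combination therapy will stop EPO if Hb ≥ 12 g/dL and continue on DFX". SAP 2.10.2 keeps that DFX-alone time in the EPO+DFX group.
- **Follow-up.** SAP 4.2.11 describes the EPO-alone responder ("This patient will hold EPO until study end") and sets the follow-up visit at 30 days after EOT, expressly not from the last non-zero dose.
- **Reporting periods.** SAP 2.10.2 reports EPO patients who do not switch for weeks 1-12, 13-24 and 1-24.
- **Exposure.** SAP 2.7.1 counts days from the first to the last non-zero administration and includes the categories 140 to <164 and ≥164 days.

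**The concern.** The rule is the same in both arms, but it acts differently. When EPO is held in the EPO-alone arm, no study drug remains, so the window closes 30 days after the last injection although the patient is still being seen. In the combination arm, daily DFX keeps the window open. Two patients with the same Hb and the same EPO hold are then counted over different lengths of time.

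The EPO-alone patient stays in the Safety Set, and SAP 2.5 bases percentages on the relevant population. The denominator is therefore unchanged while later AEs cannot enter the numerator. The distortion has one direction: it lowers EPO-alone incidence and makes the combination look relatively worse on the tolerability objective. It is sharpest in the EPO weeks 13-24 summary.

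**Working it through.** **Inputs**
- Weekly EPO from Day 1, so doses fall on Days 1, 8, 15, … (protocol 6.1.1).
- Visits with Hb at which a hold can be triggered: V5, V7, V8, V9, V10, V11 and V12 (protocol 7.2.2.4.1), on nominal Days 14, 28, 42, 56, 84, 112 and 140 (SAP Table 4-1). V8 takes place only after an EPO increase.
- EOT visit on nominal Day 168 (SAP 4.2.11). Check against the planned duration: 24 × 7 = 168.
- Follow-up of patients on hold: 168 + 30 = about Day 198.

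**Formulae**
- Last dose = latest weekly dose day on or before the triggering visit.
- Window end = last dose + 30.
- Gap = 168 (or 198) − window end.
- Weeks 13-24 are Days 85-168, which is 84 days. Days covered = window end − 84, with a minimum of 0.

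**EPO-alone patient on hold**

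| Hold triggered at | Last EPO dose | Window end | Days uncovered to EOT (Day 168) | Days uncovered to Day 198 | Days covered of the 84 in weeks 13-24 |
|---|---|---|---|---|---|
| V5 (Day 14) | 8 | 38 | 130 | 160 | 0 |
| V7 (Day 28, week 4) | 22 | 52 | 116 | 146 | 0 |
| V8 (Day 42) | 36 | 66 | 102 | 132 | 0 |
| V9 (Day 56, week 8) | 50 | 80 | 88 | 118 | 0 |
| V10 (Day 84, week 12) | 78 | 108 | 60 | 90 | 24 |
| V11 (Day 112) | 106 | 136 | 32 | 62 | 52 |
| V12 (Day 140) | 134 | 164 | 4 | 34 | 80 |

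Example for week 4: 22 + 30 = 52, and 168 − 52 = 116.

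**Sensitivity.** If one more weekly injection is given before the hold takes effect, each window ends 7 days later. A V9 hold then covers 3 of the 84 days instead of 0, and a V12 window ends on Day 171, after EOT.

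**Combination patient with the same hold.** Last DFX dose on Day 168, so the window ends on 168 + 30 = Day 198 and the gap is 0.

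**Exposure.** The 24th weekly injection falls on Day 1 + 7 × 23 = 162. SAP 2.7.1 gives 162 − 1 + 1 = 162 days, which is in 140 to <164. Counting to the last injection + 6 days gives 168 days, which is in ≥164.

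**Average EPO dose (SAP 2.7.2.2), 40,000 units/week with full compliance**
- Both terms end on Day 162: 40,000 × (162/7) ÷ (162/7) = 40,000.
- Both terms end on Day 168: 40,000 × 24 ÷ 24 = 40,000.
- Only the denominator extended: 40,000 × (162/7) ÷ 24 = 38,571.

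The end date must therefore change in both terms or in neither.

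**The case against.** **The SAP says on-study, and a patient on hold is on study.** This is the strongest point. On a plain reading of SAP 2.10.2, the late AEs would be tabulated and the gap would vanish. But the same sentence equates on-study AEs with treatment-emergent AEs, the only periods that the SAP defines are those in 2.10.1, and the protocol says on-treatment. What stands is that the wording is ambiguous and needs a definition.

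**Last dose + 30 days follows exposure, and the two patients are not alike.** The EPO-alone patient takes nothing, while the combination patient takes DFX daily. That is a fair reason for the usual convention, and SAP 2.10.1 plans a listing column for true treatment at onset that includes no treatment. It does not justify unequal counting in a comparison by arm, nor a weeks 13-24 EPO summary to which some patients in the denominator cannot contribute.

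**EOT may itself mean the last drug day.** SAP 4.2.5 defines end of treatment that way. Under that meaning, the contrast that SAP 4.2.11 draws between EOT and the last non-zero dose would be empty, so 4.2.11 must mean the visit.

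**EPO may be resumed.** Protocol Appendix 3, which is cited for dose changes, resumes EPO once Hb is below 12 g/dL; protocol 4.1 holds it until the end of study. These passages conflict. A resumed dose would shorten the gap.

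**Stronger readings that the documents do not support**
- *Patients on hold leave the AE tables.* They do not. They stay in the Safety Set, and only their later AEs go untabulated, though still listed.
- *The loss is always months.* Holds at V11 and V12 lose 32 and 4 days before EOT.
- *A percentage shortfall in EPO-alone incidence can be stated.* It would need the number held, the timing of holds and an AE rate, and the documents do not give these.
- *The ≥164-day category can never be reached.* A 24th injection two days late falls on Day 164. It is out of reach only with on-schedule dosing.

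**Conclusion.** The asymmetry follows from the plan's own definitions. For an EPO-alone hold at week 4, 8 or 12, the counted window ends 116, 88 or 60 days before EOT; a combination patient with the same hold loses none. A hold at V5 to V9 leaves essentially none of weeks 13-24 covered. EPO-alone AEs are therefore under-counted relative to the combination, by an amount that cannot be computed from the documents.

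This rests on four assumptions: on-schedule weekly dosing; EPO held to the end of study as protocol 4.1 says; DFX taken to about Day 168; and on-study meaning the on-treatment period of SAP 2.10.1. SAP 4.2.11 deals with the same situation for the follow-up visit, but the AE period has no matching rule. The plan should be corrected. The exposure point is secondary: it shifts a descriptive category, and the average dose is right as long as its two terms share an end date.

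**What to change.** 1. **Safety period.** For AE and laboratory summaries in both arms, define the period as first dose to the later of (a) last dose + 30 days and (b) for patients kept on study during a per-protocol EPO hold, the EOT visit + 30 days. Say *EOT visit*, so that SAP 4.2.5 does not turn the anchor back into the last drug day.
2. **Terminology.** Define *on-study* in SAP 2.10.1 and 2.10.2 as this period, or replace the term. Apply it to the laboratory shift tables too: protocol 10.5.11.3 uses the worst on-treatment value and SAP 2.10.3 the most extreme post-baseline result.
3. **Protocol.** Record the departure from protocol 10.5.11.1, which has the present definition.
4. **EPO hold.** Reconcile Appendix 3 with protocol 4.1 and 6.1.4 on whether EPO is resumed.
5. **EPO exposure.** In SAP 2.7.1, end EPO exposure at the last injection + 6 days. In SAP 2.7.2.2, apply that end date to the dose-duration terms in the numerator as well as to the denominator.

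**Cost.** SAP text changes, a note on the protocol departure and reprogrammed period flags. No new data are needed, because protocol Table 7-1 already schedules AE collection through EOT and the 30-day follow-up. The downside is that some AEs long after the last EPO dose will be tabulated under EPO; the planned true-treatment column identifies them.
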